- Evaluation of the number of cycles for the detection of SARS-CoV-2 viral load by RT-PCR and application of the standard curve for viral load calculation; [Period: until D15, D21 and D28, approximately 14-30 days].
- Analysis of the relationship between the calculated viral load and the clinical progress of participants in the AZVUDINE (FNC) group compared to the control group; [Period: until D15, D21 and D28, approximately 14-30 days].
- Time and proportion of lung imaging improvement during treatment (Pattern of ground-glass opacities, mosaic paving, alveolar consolidation, reticular pattern/septal thickening, opacity with inverted halo, pleural/pericardial effusion, fibrosis and/or lymphadenomegaly); [Period: until D15, D21 and D28, approximately 14-30 days].
- Time of improvement and proportion of respiratory symptoms and signs during treatment (Lung rales,

- cough, sputum, sore throat); [Period: until D15, D21, and D28, approximately 14-30 days].
- Time to normalization of O2 saturation (above 95%);
 [Period: until D15, D21 and D28, approximately 14-30 days].
- Time to normalization of respiratory rate to levels ≤ 24rpm, in room air; [Period: until D15, D21 and D28, approximately 14-30 days]
- Frequency of supplemental oxygenation or noninvasive ventilation; [Period: until D15, D21 and D28, approximately 14-30 days].
- Frequency of invasive mechanical ventilation or extracorporeal membrane oxygenation (ECMO); [Period: until D15, D21 and D28, approximately 14-30 days].
- Proportion of moderate cases that progressed to severe cases requiring intensive care unit (ICU) care; [Period: until D15, D21, and D28, approximately 14-30 days].
- Length of hospital stay; [Period: until D15, D21, and D28, approximately 14-30 days].
- Occurrence of drug interactions; [Period: until D15, D21 and D28, approximately 14-30 days].
- Frequency and intensity of adverse events; [Period: until D15, D21 and D28, approximately 14-30 days].

	 Frequency and intensity of unexpected adverse events; [Period: until D15, D21 and D28, approximately 14-30 days]. Frequency and intensity of serious adverse events; [Period: until D15, D21 and D28, approximately 14-30 days]. All-cause mortality rate during the study; [Period: until D15, D21 and D28, approximately 14-30 days]. Evaluate the tolerability of AZVUDINE (FNC) use at 			
	5mg/day regimen for up to 14 days: [Period: until D15,			
	approximately 14 days].			
	 Calculating treatment adherence; 			

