2.5. CLINICAL STUDIES WITH COVID-19

FNC-Hope1 was a randomized, open-label, controlled clinical trial to evaluate the safety and efficacy of AZVUDINE tablets in the treatment of COVID-19, conducted at *People's Hospital of Guangshan County*, China.

Twenty individuals with COVID-19 with mild to moderate symptoms were randomly and equally assigned to 2 groups, experimental and control. Subjects who received conventional treatment with FNC + (no antiviral drugs) after diagnosis **reduced** the time to become nucleic acid negative for the first time by -7.3 days, compared to those who received conventional treatment alone (9.8). Subjects who received conventional treatment + FNC (no antiviral drugs) reduced the time to nucleic acid

negative for the first time by -6.8 days compared to those who received conventional treatment alone (11,30).

[figure not shown]

Figure 3: Kaplan-Meier curves of two consecutive negative tests for SARS-CoV-2 (a) first and b) second) in FNC and control group. Data are percent (%). Differences between groups were using the Log-rank test (Mantel-Cox)

On the fourth day after treatment, the rate of the first negative nucleic acid conversion reached 100% in patients in the FNC group and 30% in patients in the control group. Kaplan-Meier curves indicate the significant difference (p = 0.0013). On day 6, the negative conversion rate of the second nucleic acid reached 100% in patients of the FNC group and 40% in patients of the control group. Kaplan-Meier curves indicate the significant difference (p = 0.0011).

Regarding the safety analysis, there was no adverse event in the experimental group and three adverse events in the control group with an incidence of 30% (3/10) during the study period. All adverse events were grade 2 and were followed up until they disappeared. There were no serious adverse events, serious adverse reactions, major adverse events, or death events during the study period. The demographics and baseline characteristics of the subjects were similar and the proportions between the 2 groups were relatively balanced and comparable.

In 3 other hospitals in China, during the periods February 14 to March 10, March 1 to March 22, and March 7 to March 30, 32 volunteers with mild to severe symptoms were treated with different antiviral therapeutic approaches, including Arbidol,

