For Early Termination (ETA) of treatment, participants should follow the routine for visit 17: End of Treatment (D15), in advance. Discharge from the hospital may be

granted before the end of the 14-day treatment period if clinically indicated and the treatment has been completed.

The period between randomization and the end of treatment will be up to 14 days and there may be early termination (AT) or worsening. Participants who, even after the end of treatment, still remain in the hospital, will undergo the procedures and tests for safety and efficacy monitoring on D21 and follow the follow-up schedule from D28 to D60.

During the follow-up period, the participant will be required to return within 28 and 60 days of hospital discharge for follow-up visits.

The first day of treatment will be day 1 and will last up to 14 days.

Treatment will be terminated early when two consecutive RT-PCR tests are negative (criteria for hospital discharge) and may be stopped early in the event of participant dropout, or in the event of EAG.

All participants will undergo efficacy and safety evaluations. Blood samples and respiratory samples (oropharyngeal and nasopharyngeal swabs) will be obtained on days D1, D3, D5, D7, D9, D11, D13, and D14 (while hospitalized); and day D21 (participants still hospitalized after completion of treatment) and days D28 and D60 (upon return to the center or if still hospitalized). Detailed information about the visit is in section 7.3.

After discharge from the hospital, research participants should follow the instructions below in accordance with the care and attention specified by the research center:

- Stay in recovery for 3 to 6 weeks;
- Use face masks when necessary;
- Sanitize your hands and do not share personal objects;
- Avoid contact with people in the risk group, especially;

• Inform the Principal Investigator, or his/her team, immediately in case of fever and/or respiratory symptoms.

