The sensitivity of each RT-PCR equipment and kit used varies in the number of CTs to generate the qualitative result (Positive or negative)¹¹.

So, to extract RELIABLE **QUANTITATIVE** data, both the equipment and the reagent kit must be standardized to avoid discrepancies. However, this is not enough, so a standard curve should provide the correlation between CTs and *viral RNA copy* number.

Therefore, we will use the QuantStudio5 RT-PCR equipment, *Applied Biosystems*, NS: 272525086, ANVISA Reg.: 10358940069, to issue reports for statistical accounting and to assist in the standard curve analysis, via dedicated software¹². We will also use the TaqPathTMCOVID-19 CE-IVD RT-PCR¹³ kit (ANVISA Reg.: 10358940107), which can provide us with the viral load-related CT values (viral RNA copies) as a function of the standard curve constructed with the positive control (TaqPath COVID-19 *Control*), which is SARS-CoV-2 viral RNA at a known concentration of 1 x 104 copies/ μ L. By means of the standard curve, using serial dilutions of the positive control, we can arrive at the

concentration (in number of copies) of the viral RNA present in each sample from the volunteers and participants.

For example, it is common to determine the concentration of proteins in a sample using a colorimetric method, the Bradford assay. Similarly, by performing serial dilutions of the positive control we can establish a standard curve (equation y = ax + b) using the CTs obtained for each point on the concentration curve.

The positive RT-PCR result occurs at CTs ≤37. In this case, when viral RNA is present, the specific probe used for detection of SARS-CoV-2 is broken by DNA polymerase, emitting fluorescence. The higher the viral RNA copy number, the higher the fluorescence and therefore the CT value appears earlier during the reaction.

The lower the copy number of the viral RNA, the lower the fluorescence and, consequently, the CT value appears later. CTs values >37 are considered negative. By establishing a curve of viral RNA concentration (present in the positive control), we will obtain a curve of CTs, from lower values (higher viral RNA copies) to higher values (lower viral RNA copies).

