² The examinations and procedures under visit 17 (D15) must be performed by all participants as soon as the treatment is terminated, including participants who have stopped treatment early (AT) and for any other reason.

³ The. procedures and examinations planned to be performed at visit D28 and D60 will be determined by the Principal Investigator according to the participants' previous examinations.

⁴ For women of childbearing age only.

⁵ Visit 18 procedures will be performed only on research participants who are still hospitalized.

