Univariate analysis of the clinical outcome variables and with the group variable.

- For the secondary efficacy indicator analysis, the coronavirus viral load changes compared to baseline should be calculated for the experimental and control groups separately, as well as the value of the difference between the viral load changes compared to baseline for both groups. The ANCOVA model will be used to estimate the impact of treatment on viral load changes adjusting for other study variables such as disease severity, age, weight, and comorbidities, etc.
 - For analysis of the secondary efficacy indicator one should stratify according to the severity of the disease (severe, severe), following the following statistical methods:

PRIMARY ENDPOINT			ANALYSIS METHOD
•	Propo	rtion of participants with clinical status	Teste t de
	impro	vement [Period: until D15,	Student/Teste de
	appro	ximately 14 days].	Mann-Whitney
	0	The criterion for a participant to have	
		an improvement in clinical status is a	
		decrease on the WHO Clinical	
		Improvement Ordinal Scale in at least	
		one category compared to screening	
		(WHO, Jun/2020).	

SEC	CONDARY OUTCOMES	
•	Proportion of participants with a clinical	Pearson's Chi-
	outcome of cure during the study; [Period:	square test
	until D15, D21, and D28, approximately 14-	
	30 days].	

;	inic	al Trial Design	
		o The clinical endpoint of cure is	Student's t-test /
		defined in this protocol as the	Mann-Whitney
		absence of viral RNA in	test
		collected samples and clinical	
		conditions for	
		hospital discharge.	
	•	Time to normalization of body temperature	Student's t-test /
		(below 37.6c, axillary); [Period: until D15,	Mann-Whitney
		D21 and D28, approximately 14-30 days].	test
		Time to improvement of diarrhea,	Student's t-test /
		myalgia, fatigue, malaise, cough and	Mann-Whitney
		headache; [Period: until D15, D21 and	test
		D28, approximately 14-30 days].	
		Changes in liver and kidney function	Student's t-test /
		baselines, and inflammatory and	Mann-Whitney
		immunological markers: [Period: until	test
		D15, D21 and D28, approximately 14-30	
		days]	
		 Lab tests performed on days D1, 	
		D3, D5, D7, D9, D13, D15, D21,	
		D28, and D60.	
		Evaluation of the time to negative	Student's t-test /
		conversion of SARS-CoV-2 viral load by	Mann-Whitney
		RT-PCR between AZVUDINE (FNC) group	test
		and placebo- control group; [Period: until	
		D15, D21 and D28, approximately 14-30	
		days].	

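### Viral-load sampling ends on the outcome itself, so the planned t-test, Mann-Whitney and ANCOVA understate a faster viral decline from about D9 onward

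*Protocol*

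**What the plan says.** The Synopsis and sections 4 and 7.1.2 name the endpoint as "Evaluation of the number of cycles for the detection of SARS-CoV-2 viral load by RT-PCR and application of the standard curve for viral load calculation", over periods to D15, D21 and D28.

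Section 5.3.2 sets the assay limit: "The positive RT-PCR result occurs at CTs ≤37" and "CTs values >37 are considered negative". Copy number is read from a standard curve. No copy number or substitute value is given for a sample beyond the limit.

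Section 11.3 assigns Student's t or Mann-Whitney to the cycle-number endpoint. For change from baseline it says "The ANCOVA model will be used to estimate the impact of treatment on viral load changes", adjusted for severity, age, weight, comorbidities and the like.

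On sampling, section 5.1.1 says blood and respiratory samples "will be obtained on days D1, D3, D5, D7, D9, D11, D13, and D14 (while hospitalized"). Footnote 5 to Table 10 adds: "Visit 18 procedures will be performed only on research participants who are still hospitalized"; visit 18 is D21. Two consecutive negative tests end treatment (5.1.1) and are one of the criteria for discharge (Synopsis). Footnote 2 to Table 10 requires the end-of-treatment visit (V17), which includes a swab, from everyone when treatment ends.

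**The concern.** The rule that ends sampling is a function of the variable being measured. A participant who clears the virus reaches two negatives, stops treatment, becomes eligible for discharge, and leaves the 48-hourly series. A participant who does not clear stays in it. The later the day, the more the available values belong to slow clearers, and a faster-clearing arm loses more of its members. The comparison at those days is no longer between the randomized groups, and the bias runs toward no difference.

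D21 shows this without any assumption: however a negative is scored, only those still in hospital have a value.

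The protocol's own pilot makes early exit plausible: "On day 6, the negative conversion rate of the second nucleic acid reached 100" per cent in the azvudine group, against 40% in control (section 2.5). That pilot had 10 patients per arm with mild to moderate disease, so it is only indicative for moderate to severe inpatients.

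At stake is the credibility of one secondary endpoint. The primary endpoint is not affected.

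**Working it through.** **The plan's own figure.** Section 11.1 sizes the trial on the primary endpoint only; no size or effect is stated for viral load. With p1 = 0.667, p2 = 0.281, margin 0.205, one-sided alpha 0.05 and 80% power: (1.645 + 0.842)² × (0.667×0.333 + 0.281×0.719) / (0.386 − 0.205)² = 80.04, so 81 per arm. Then 81/0.90 = 90 per arm, 180 in total. This reproduces, and here it only supplies the 81 per arm used below.

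**Illustration on Ct.** The protocol gives no viral course, so every Ct input is assumed: baseline Ct mean 25 (SD 4), measurement SD 1.5, 81 per arm, 48-hourly swabs, negative if Ct > 37, exit after two consecutive negatives, 600 simulated trials per scenario. Each cell is the treated-minus-control difference in Ct change among those still positive, divided by the true difference in everyone.

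| Ct rise/day, control vs treated (slope SD) | D5 | D7 | D9 | D13 |
|---|---|---|---|---|
| 1.0 vs 1.3 (0.5) | 1.06/1.14 = 93% | 1.46/1.74 = 84% | 1.64/2.33 = 70% | 1.69/3.50 = 48% |
| 1.0 vs 1.5 (0.5) | 1.85/1.97 = 94% | 2.46/2.97 = 83% | 2.81/3.95 = 71% | 2.83/5.91 = 48% |
| 1.0 vs 1.5 (0.2) | 1.94/2.00 = 97% | 2.79/3.00 = 93% | 3.48/3.97 = 88% | 4.48/5.98 = 75% |
| 0.8 vs 1.2 (0.4) | 1.53/1.59 = 96% | 2.12/2.38 = 89% | 2.51/3.17 = 79% | 2.83/4.77 = 59% |

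At D13, in the same row order:
- Still positive, treated vs control: 31% vs 50%, 21% vs 50%, 11% vs 50%, 35% vs 64%.
- Power among positives, t-test on change: 31%, 56%, 97%, 83%.
- Power among positives, Mann-Whitney on Ct: 15%, 23%, 29%, 42%.
- Power of Mann-Whitney on everyone, negatives tied at the limit: 73%, 99%, about 100%, 99%.

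**Illustration on log10 copies.** Assumed: baseline 6 log10 (SD 1.5), fall of 0.4 vs 0.6 log10 per day, limit 2 log10. The true difference at D13 is (0.6 − 0.4) × 12 days = 2.4 log10. An ANCOVA of change among positives has power of 99-100% at D7, 82-94% at D9 and 19-27% at D13, depending on the person-to-person and measurement variation assumed. Its D13 estimate is about −0.7, which is 0.7/2.4 = 29% of the truth.

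**What this implies for the remedy.**
- Plugging in the limit and comparing means does not repair the estimate. At D13 on the Ct scale it gives 1.35, 2.01, 1.66 and 2.32, each smaller than the positives-only difference in the table. A value beyond the limit has to be modelled as censored.
- An unadjusted rank test on everyone is not the best main analysis at an early day. At D7 its power is 54%, 95%, 98% and 84%, against 68%, 98%, 100% and 98% for the t-test on change among positives.

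**The case against.** A reader might infer three stronger things that the documents do not support.

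- *Swabs stop at discharge.* Section 5.1.1 goes on to schedule samples at D28 and D60 on return to the center, Table 10 appears to mark RT-PCR at D28, and V17 takes a last swab from everyone. What stops is the 48-hourly series and D21. The D28 and D60 swabs are themselves uncertain: the V19 and V20 lists in 7.3 name none, footnote 3 to Table 10 leaves those procedures to the investigator, and the Synopsis lists discharge after two negatives as ending participation. They would not restore the days from D7 to D21 in any case.
- *Negative samples have no value and are dropped.* No passage excludes them. Section 5.3.2 speaks of Ct values above 37 as values that are classed negative. The positives-only analysis above is therefore the adverse reading, though a natural one, since nothing says what copy number such a sample receives.
- *Faster clearance is hidden, and power falls as the effect grows.* Time to negative conversion and cure are separate secondary endpoints. The positives-only estimate kept the right sign in every scenario. At D7 in the log10 illustration, rate gaps of 0.1, 0.2 and 0.3 per day gave growing estimates (−0.48, −0.89, −1.28) and rising power (65%, 99%, 100%).

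It is also fair to say that two negatives are only one discharge criterion, that discharge needs medical evaluation (9.1), and that handling values beyond a detection limit is often left to the statistical analysis plan. The last point only partly answers the concern. The Synopsis refers to chapter 11 for detailed methods, and 11.3 names the tests. Those named tests, on the stated sampling, are what give an attenuated late comparison.

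**Conclusion.** The concern holds in a limited form. Sampling thins because of the outcome, so t-test, Mann-Whitney or ANCOVA on available values understates a faster decline at later days. Under the assumed courses the loss is small at D5, moderate at D7 (83-93% of the true difference kept on the Ct scale), and serious by D13 (48-75% kept on Ct; about 29% with ANCOVA on log10 copies). The direction follows from the text. The size rests on assumed viral courses and on negatives not entering the comparison. D21 is selected on hospital stay whatever the scoring. The matter is confined to secondary viral-load endpoints and deserves correction because the change is cheap.

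**What to change.** In section 11.3, and in the statistical analysis plan:

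1. Analyse log10 copies in all treated participants at one fixed early day, such as D5 or D7, named in advance.
2. Treat Ct above 37 as left-censored at the copy number equivalent to Ct 37. Do not give it a plugged-in value in a comparison of means.
3. For participants who stopped after two consecutive negatives, carry that censored value to the later planned in-hospital days.
4. Use a censored-normal (Tobit) ANCOVA adjusted for baseline viral load as the main method, with a rank test as sensitivity analysis. Report positives-only means as descriptive.

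Separately, reconcile the D28 and D60 swab between 5.1.1, the V19 and V20 lists in 7.3, Table 10 with its footnote 3, and the Synopsis entry that treats discharge as the end of participation.

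The cost is wording only; no new samples are needed. There are two assumptions to state: no viral rebound after two negatives, and approximate normality on the log scale. The second matters most at late days, when most values are censored, and is a further reason to make an early day the main one.

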1. SUMMARY

1.1. SYNOPSIS

	Evaluation of the Safety and Clinical Efficacy of AZVUDINE in
TITLE	patients infected with SARS-CoV-2 virus: a Phase III,
	randomized, double-blind, PLACEBO-controlled study.
STUDY ID	IGZ-1
DOCUMENT TYPE	Phase III Clinical Trial Design
VERSION/ISSUANCE DATE	Version 0.5 of May 30, 2022
	HRH HOLDINGS LIMITED, [name]
SPONSOR	[name]
	[name].
	INSTITUTO GALZU DE PESQUISA, ENSINO, CIÊNCIA E
	TECNOLOGIA APLICADA, CNPJ: 28.831.817/0001-20.
	Office: [name], Zip Code:
REPRESENTATIVE	[name], Campos dos Goytacazes-RJ.
ORGANIZATION OF	Interface Hospitalar: [name],
CLINICAL RESEARCH	[name], Hospital Santa Casa de
SPONSOR IN BRAZIL (ORPC)	Misericórdia de Campos, [contact] Ext.
	180/194
	Contact [name] [name]
	Site: http://www.institutogalzu.org.br
	E-mail: [contact]
CTUDY CITE	Santa Casa de Misericórdia de Campos, Campos dos
STUDY SITE	Goytacazes - RJ

	Primary Goal
OBJECTIVE	 To evaluate the efficacy and safety of AZVUDINE (FNC) versus placebo in patients infected with moderate to severe stage SARS-COV-2; Secondary objective
	 To evaluate the clinical outcome between the AZVUDINE (FNC) group versus the PLACEBO group in patients infected with moderate to severe stage SARS- COV-2;
INTERVENTION	 Experimental group: AZVUDINE 5mg/day, orally for up to 14 days + Standard treatment. Control group: PLACEBO orally for up to 14 days + Standard treatment.
NUMBER OF PARTICIPANTS	Following initial study data, the sample size calculation was revised updating parameters of frequency of clinical improvement and dropout rate. The revised sample size is 180 participants randomly and equally divided into the two arms of the study (90 practitioners in each group).

The study consists of 3 periods: **screening, treatment, and follow-up.** In the screening period, patients who meet the eligibility criteria will be enrolled in the study and randomized into one of the two study arms, experimental or control. The first day of treatment will be day 1, and will last up to 14 days.

STUDY DESIGN

Treatment will be terminated early when two consecutive RT-PCR tests are negative (one of the criteria for hospital discharge). Treatment will also be stopped early in the event of participant dropout or in the event of an EAG.

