- Time and proportion of lung imaging improvement during treatment (Pattern of ground-glass opacities, mosaic paving, alveolar consolidation, reticular pattern/septal thickening, opacity with inverted halo, pleural/pericardial effusion, fibrosis and/or lymphadenomegaly); [Period: until D15, D21 and D28, approximately 14-30 days].
- Time of improvement and proportion of respiratory symptoms and signs during treatment (Lung rales, cough, sputum, sore throat); [Period: until D15, D21, and D28, approximately 14-30 days].
- Time to normalization of O2 saturation (above 95%);
 [Period: until D15, D21 and D28, approximately 14-30 days].
- Time to normalization of respiratory rate to levels ≤ 24rpm, in room air; [Period: until D15, D21 and D28, approximately 14-30 days]
- Frequency of supplemental oxygenation or non-invasive ventilation; [Period: until D15, D21 and D28, approximately 14-30 days].
- Frequency of invasive mechanical ventilation or extracorporeal membrane oxygenation (ECMO); [Period: until D15, D21, and D28, approximately 14-30 days].

- Proportion of moderate cases that progressed to severe cases requiring intensive care unit (ICU) care; [Period: until D15, D21, and D28, approximately 14-30 days].
- Length of hospital stay; [Period: until D15, D21 and D28, approximately 14-30 days].
- Occurrence of drug interactions; [Period: until D15, D21 and D28, approximately 14-30 days].
- Frequency and intensity of adverse events; [Period: until D15, D21 and D28, approximately 14-30 days].
- Frequency and intensity of unexpected adverse events;
 [Period: until D15, D21 and D28, approximately 14-30 days].
- Frequency and intensity of serious adverse events;
 [Period: until D15, D21 and D28, approximately 14-30 days].
- All-cause mortality rate during the study; [Period: until D15, D21 and D28, approximately 14-30 days].
- Evaluate the tolerability of AZVUDINE (FNC) use at 5mg/day regimen for up to 14 days: [Period: until D15, approximately 14 days].
 - Calculating treatment adherence;
 - Total time of use of AZVUDINE (FNC);
 - Proportion of participants who withdrew consent;
 - Proportion of participants who dropped out of treatment.

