6.2.4. Dose and method of administration

Research participants will be randomized 1:1 to receive the experimental drug or PLACEBO. Each dose of AZVUDINE or PLACEBO will be administered by the research team member qualified and delegated for this role. The administration, date and time,

will be entered into the study eCRF.

AZVUDINE will be administered orally at a dose of 5mg, once daily, while the participant is hospitalized, for up to 14 days of the full course or until two consecutive negative viral load tests are obtained by RT-PCR.

Research participants will be instructed to swallow the medication whole, without breaking, chewing, crushing, or dividing it before ingesting it. The dose should preferably be given at the same time to all participants every day.

The corresponding PLACEBO will be given in equal amounts, at the same time and respecting the same guidelines described above, to the participants who are allocated to the PLACEBO group.

According to the "Clinical study on the postprandial pharmacokinetics of AZVUDINE" (GQ-FNC-105, Henan Genuine Biotechnology Co, Ltd.), conducted in Beijing You'an Hospital affiliated with Capital Medical University, under the responsibility of [name], in the period from Dec-2015 to May-2018, which is one of the reference of studies related to the preliminary stages of clinical development of AZVUDINE (FNC), the incidence of adverse effects observed in both regimens of experimental drug administration (fasting X postprandial) were similar to each other. All AEs were grade 1 in intensity, requiring no therapeutic management measures, thus demonstrating that the FNC administration regimen does not compromise the safety and tolerability of the investigational drug in healthy subjects.

The experimental drug should be administered daily at 8 pm to minimize the risk of falling, since in preliminary studies, it was observed that vertigo (incidence ≥5%) appears to be an AE likely related to FNC. However, no restrictions on meals.

The total course should not exceed 14 calendar days, even if a dose has been missed. The **lost** investigational product, if it occurs, should follow the principle of "whether the lost medication schedule exceeds 1/2 medication interval or not." If the missed medication schedule is within the first 12 hours of the interval between two medications, the missed investigational product can be re-administered normally and

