VISIT 3-16: PROCEDURE (D1-D14)

The treatment period will start on D1 according to randomization.

The treatment will last up to 14 days, and may be stopped early in case of treatment success (2 consecutive negative RT-PCR tests), participant dropout, or at the Principal Investigator's option, if deemed necessary for the safety of the participant.

For the **Early Termination (ETA)** of treatment, participants should follow the routine from visit 17: End of Treatment (D15), in advance.

The Principal Investigator for the study will be available to answer any questions.

The experimental drug should be administered daily at 8 pm to minimize the risk of falling, since in preliminary studies, it was observed that vertigo (incidence ≥5%) appears to be an AE likely related to FNC. However, no restrictions on meals.

The following procedures will be performed in the V3-16 visits:

- Administration AZVUDINE or PLACEBO daily, at the same time at 8pm, to minimize the risk of falling, since in preliminary studies, it was observed that vertigo (incidence ≥5%) may be an AE likely related to FNC;
- Monitoring drug interactions and AEs on a daily basis;
- Monitoring symptoms, vital signs, oximetry and blood glucose daily;
- Collection of blood samples and respiratory sample (nasal and oropharyngeal swab) for safety and efficacy monitoring tests every 48h);
- CT scan of the lung every 4 days and electrocardiogram on days D1 and D11;

The Principal Investigator may adjust the procedures performed during treatment according to the condition of the research participant and the results of clinical examinations.

VISIT 17: END OF TREATMENT (D15)

At the end of treatment or discontinuation of the investigational drug or PLACEBO, all participants will be required to undergo procedures and tests for safety and efficacy monitoring. The procedures should be performed before discharge from the hospital approximately 24 hours after the administration of the last dose of the investigational drug or PLACEBO, because for the 5 mg dose of AZVUDINE, the mean half- life is 13.8 hours, and it is excreted in the urine within 24 hours.

The treatment will last up to 14 days, and may be stopped early in case of

treatment success (2 consecutive negative RT-PCR tests), participant dropout, or at the Principal Investigator's option, if deemed necessary for the safety of the participant.

The following procedures will be performed at the V17 visit:

- Monitoring drug interactions and AEs;

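### Lung-imaging and respiratory-sign improvement carries two conflicting windows, and the one tied to treatment is set by viral clearance, which azvudine is expected to change

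*Protocol*

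**What the plan says.** Two secondary endpoints name treatment as the observation window: "Time and proportion of lung imaging improvement during treatment" and "Time of improvement and proportion of respiratory symptoms and signs during treatment". The period attached to each is "Period: until D15, D21 and D28, approximately 14-30 days". Both appear with both windows in section 1.1 (synopsis), section 4, section 7.1.2 and the table of methods in section 11.3.

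Treatment has no fixed length. Section 6.2.4 gives it "for up to 14 days of the full course or until two consecutive negative viral load tests are obtained by RT-PCR", and the synopsis says "Treatment will be terminated early when two consecutive RT-PCR tests are negative".

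The scan schedule in section 7.3 is "CT scan of the lung every 4 days and electrocardiogram on days D1 and D11". As Table 10 reads, CT falls on D1, D3, D7, D11, D15, D21 and D28. Its footnotes bring the visit 17 (D15) examinations forward to the end of treatment for anyone who stops early, restrict visit 18 (D21) to inpatients, and leave the D28 and D60 procedures to the investigator.

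Section 11.3 assigns Student's t or Mann-Whitney to the time part of each endpoint and Pearson's chi-square to the proportion.

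**The concern.** A window that ends with treatment cannot also run to D21 and D28, because treatment lasts 14 days at most. The definition therefore contradicts itself.

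The treatment window also closes when the virus clears. Section 2.6.3 expects azvudine to bring clearance forward. If it does, treated participants have fewer days, and fewer scans, in which improvement can be recorded. As Table 10 reads, stopping around day 5 leaves two post-baseline CTs (D3 and the advanced end-of-treatment scan), against four for a full course (D3, D7, D11, D15). The comparison would then partly measure the length of observation rather than the state of the lung.

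**Working it through.** **The plan's own figure.** The protocol states no rates or power for these endpoints. The one figure borrowed is the 81 evaluable per group in section 11.1, which reproduces:

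[0.667×0.333 + 0.281×0.719] × (1.645 + 0.8416)² / (0.386 − 0.205)² = 0.42415 × 6.183 / 0.032761 = 80.04, so 81; 81/0.9 = 90.

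This uses the one-sided 5% value, which is a separate matter.

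**Inputs.**
- Window lengths. Section 2.5 reports that azvudine shortened time to nucleic acid "negative for the first time by -6.8 days compared to those who received conventional treatment alone", whose time was 11.30 days. That gives 11.3 − 6.8 = 4.5 against 11.3 days. Treating these as times to the second negative test is an assumption, since the text labels them first-negative. It is plausible because the other first-negative figure has a different control time (9.8 days), and because of the conversion rates that section 2.5 gives for the sixth day: "the negative conversion rate of the second nucleic acid reached 100% in patients of the FNC group and 40% in patients of the control group".
- Time to improvement: assumed exponential with the same median m in both arms, so no effect on the lung. Section 11.1 gives 7 days as the control median for clinical improvement; the range 5-14 is assumed.
- Tests: two-sided 5%, as in section 11.3, with 81 per arm.

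**Step 1: the same fixed window for everyone in an arm.** Proportion improved by day t = 1 − 0.5^(t/m).

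| m (days) | Azvudine, t = 4.5 | Placebo, t = 11.3 | Chance of significance against azvudine | Both arms by day 28 |
|---|---|---|---|---|
| 5 | 46% | 79% | 99% | 98% |
| 7 | 36% | 67% | 98% | 94% |
| 10 | 27% | 54% | 95% | 86% |
| 14 | 20% | 43% | 89% | 75% |

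**Step 2: clearance varying between participants.** 1,500 simulated trials per row, with gamma clearance times capped at 14 days, scans on D3, D7, D11 and at treatment end, and the same improvement hazard in both arms. The last column compares recorded times among improvers only, by Mann-Whitney. The nominal rate in either direction is 2.5%.

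| Mean clearance, azvudine v placebo (days) | m | Proportion improved | False harm (proportion) | False benefit (time) |
|---|---|---|---|---|
| 4.5 v 11.3 | 7 | 38.7% v 60.3% | 79% | 83% |
| 4.5 v 11.3 | 14 | 22.0% v 38.4% | 63% | 67% |
| 7 v 9 | 7 | 49.4% v 55.3% | 11% | 12% |
| 7 v 9 | 14 | 29.5% v 34.4% | 9% | 10% |
| 8 v 9 | 7 | 52.3% v 55.3% | 5% | 5% |
| 8 v 9 | 14 | 32.1% v 34.2% | 5% | 4% |
| 11.3 v 11.3 | 7 | 60.5% v 60.3% | 2.0% | 3% |
| 11.3 v 11.3 | 14 | 38.5% v 38.1% | 2.2% | 2% |

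Time moves in the opposite direction because a short window admits only early improvers. With clearance of 4.5 v 11.3 days and m = 7, the mean recorded time is 4.2 days on azvudine and 6.3 on placebo.

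**Step 3: a common window.** With improvement fully observed to day 14 in everyone, both arms are at 75% (m = 7) or 50% (m = 14). The two-sided rejection rate across the scenarios is 4.6-6.3%, nominal within simulation error.

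**The case against.** The calendar bracket is the more natural time frame. It is attached to nearly all the secondary endpoints, and CT is scheduled at D21 and D28, which would serve no purpose for these endpoints if observation ended with treatment. A statistical analysis plan, not shown here, may settle the matter. This makes the treatment reading less likely, but the protocol does not exclude it. Neighbouring endpoints such as oxygen saturation and respiratory rate carry only the calendar period, so the extra words in these two look deliberate.

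The size is also open to challenge, and this objection stands. HOPE-1 was an open-label study of 20 patients with mild to moderate disease, whereas this trial enrols hospitalised moderate-to-severe patients. The 4.5 and 11.3 days rest on an assumed reading of its figures. The clearance gap drives the result, and a gap of 1-2 days brings false harm down to about 5-11%.

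A reader might infer more than the documents support:
- That an inert drug would look harmful. It would not: without an antiviral effect the windows are equal and the error rate is nominal (last two rows of step 2).
- That azvudine's window is shorter as a matter of design. It is shorter only if the drug speeds clearance.
- That the whole endpoint is tilted against azvudine. Only the proportion is; time among improvers tilts the other way.
- That the two windows give opposite results. In this model the proportion shows a deficit under one and equality under the other.

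**Conclusion.** The point holds as a contradiction in the definition of two secondary endpoints, with a conditional bias under one of the two readings. If azvudine clears virus faster and has no effect on the lung or respiratory signs, the treatment window biases the proportion improved against it and time among improvers in its favour, so the two halves of one endpoint can disagree.

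With exponential improvement times and 81 per arm, false harm ranges from 89-98% (medians 7-14 days, fixed windows of 4.5 and 11.3 days), through 63-79% (variable clearance with those means), to about 5-11% (means 1-2 days apart). The result on time assumes that only improvers are compared.

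The calendar reading is not fully secure either. An early finisher who has been discharged has no scheduled CT between treatment end and the D28 visit, so there is no common D15 CT. The primary analysis and the sample size are unaffected.

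**What to change.** 1. Delete the treatment wording from both endpoints in sections 1.1, 4, 7.1.2 and 11.3. Count improvement from D1 to a stated calendar day in every participant, whatever the day treatment stopped.
2. For CT, make the D28 scan the common time point, anchored to start of treatment. Table 10 counts D28 from start of treatment, but visit 19 in section 7.3 places it two weeks after discharge; these must be reconciled. Exempt this CT from the investigator discretion in footnote 3 of Table 10.
3. Do not treat the advanced visit 17 CT of an early finisher as a D15 value.

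The wording change is nearly free. The real cost is that the D28 CT becomes mandatory, and that a common D15 CT comparison is lost unless early finishers are rescanned on that day. Dosing and the treatment-stopping rule are not touched.
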